Multiple sclerosis (MS) is a chronic, autoimmune disease that causes inflammation and destruction of the brain and spinal cord. This condition is the leading cause of non-traumatic disability among young adults, and affects nearly half a million Americans and 2.5 million people worldwide. In addition to physical disability, MS patients suffer disproportionately from a variety of complications that negatively impact quality of life, including cognitive dysfunction, and sleep disturbances.

Cognitive dysfunction is one of the most common and consequential symptoms of MS. Impairments in processing speed, working memory, learning, executive function, visual-spatial processing, and language function affect 42-70% of MS patients, and constitute a major cause of loss of employment, caregiver stress, and reduced quality of life.¹⁻⁵ Despite the high prevalence and consequences of cognitive dysfunction in MS, the identification of appropriate strategies to minimize its impact is hindered by a poor understanding of factors that influence its severity, or common medical comorbidities that may increase patients' vulnerability to its effects.

Obstructive sleep apnea (OSA) is a common disorder characterized by repeated episodes of upper airway obstruction during sleep. Growing evidence suggests that nocturnal hypoxia caused by OSA contributes to cognitive dysfunction in the general population,⁶⁻¹⁰ and that treatment for OSA in the form of positive airway pressure (PAP) therapy may improve cognitive dysfunction in individuals who do not have MS.^{11, 12} Yet, the relationship between cognition and sleep apnea remains virtually unstudied in patients with MS. This is a critical gap in knowledge, as our recent data suggest that at least one fifth of MS patients carry a diagnosis of OSA, while a substantially higher proportion of patients (more than half) may have undiagnosed OSA. Furthermore, new data from our group suggest that OSA severity is closely related to reductions in cognitive performance in MS subjects.¹³ These preliminary findings indicate that OSA could contribute to domains of cognitive dysfunction that are key aspects of morbidity in MS. Larger, prospective studies are now needed to demonstrate the nature and directionality of the relationship between sleep disordered breathing and cognitive dysfunction in individuals with MS. If a causal role does exist, identification and treatment of OSA could provide new opportunities improve cognition in persons with MS.

Objectives, Aims, and Endpoints

The objectives of this randomized, rater-blinded clinical trial are to 1) determine the effects of OSA on specific domains of cognitive function in patients with MS; and 2) assess the effects of OSA treatment with positive airway pressure (PAP) therapy on cognitive dysfunction in MS patients.

For Aim 1, subjects with MS (n~175) who screen positive on a commonly used screening tool for OSA (STOP-Bang questionnaire)¹⁴ or who have a preexisting diagnosis of OSA but are not yet using PAP compliantly will undergo baseline cognitive testing and standard nocturnal polysomnography (PSG). For subjects who have a recent diagnosis of OSA based on recent (within 1 year) in-lab clinical University of Michigan Sleep Laboratory PSG who have not yet started using PAP treatment compliantly, their in-lab clinical PSG data will be used for baseline

analyses. After adjustment for clinical confounds and other PSG outcomes, we will assess the extent to which apnea severity as reflected by baseline PSG contributes to cognitive dysfunction in MS.

For Aim 2, subjects who meet criteria for OSA on baseline PSG or recent U-M Sleep Lab in-lab clinical PSG (n~140) will be randomized into one of 2 groups: expedited positive airway pressure (PAP) therapy, followed by repeat cognitive testing at 3 months post-PAP (Group 1, n~93), or standard care PAP therapy which will commence following completion of month 3 testing (Group 2, n~47). Mean changes from baseline in cognitive test scores will be compared between groups.

Assessments

The aims of this study are to assess the relationship between sleep apnea severity and cognitive dysfunction in MS patients with OSA (Aim 1), and to examine the effects of positive airway pressure (PAP) on cognitive function in MS patients with OSA (Aim 2).

N~175 patients who screen positive for high OSA risk on a validated screening questionnaire (STOP-Bang), or who already carry a diagnosis of OSA but are not yet using PAP on a compliant basis will be invited to participate.

Consenting subjects with STOP-Bang scores positive for ≥ 2 risk factors for sleep apnea who are at high risk for OSA but who do not yet have a University of Michigan Sleep Laboratory PSG will undergo baseline (month 0) in-lab PSG and baseline neuropsychological (cognitive) testing. Subjects who have a recent diagnosis of OSA based on recent (within 1 year) in-lab clinical University of Michigan Sleep Laboratory PSG who have not yet started using PAP treatment compliantly will undergo baseline cognitive testing and their in-lab clinical PSG data will be used for baseline analyses. Subjects who have a diagnosis of OSA based on non-UM in-lab PSG or PSG > 1 year prior to screening will undergo new baseline PSG and baseline cognitive testing.

Subjects who meet criteria for OSA on baseline or clinical PSG (n~140, anticipated) will then be randomized into one of 2 groups (2:1 randomization): immediate treatment with PAP (Group 1, n~93) followed by repeat neuropsychological testing at 3 months post-PAP; or standard of care application of PAP at 3 months, after completion of repeat neuropsychological testing (Group 2, n~47). Analyses will focus on relationships between standard PSG measures (including the Respiratory Disturbance Index, oxygen desaturation index, and minimum oxygen saturation), innovative new quantitative PSG measures and cognitive test scores, as well as mean changes from baseline in individual and composite cognitive test scores following treatment with PAP therapy.

Statistical Methods

Analyses will focus on relationships between standard PSG measures (Respiratory Disturbance Index, oxygen desaturation index, and minimum oxygen saturation), innovative new quantitative PSG measures and cognitive test scores, as well as mean changes from baseline in individual cognitive scores following treatment with PAP therapy.

For aim 1, multivariate linear regression models will be used to analyze the effects of PSG-derived standard measures of sleep disordered breathing (including RDI, ODI, minimum O2 saturation), on individual cognitive test scores (continuous outcome variables of interest, in separate models). For Aim 2, multivariate linear regression models will be used to test the effects of Group effect on 3-month (“post”) cognitive test scores, controlling for baseline (“pre”) test scores and other covariates. We will also examine the association of PAP use as a continuous variable, based on mean nightly hours of use per month, on 3-month individual cognitive test scores, controlling for baseline scores.

1. INTRODUCTION

1.1 Indication

The proposed study will assess the relationship between obstructive sleep apnea severity and cognitive dysfunction in MS patients with OSA (Aim 1), and examine the effects of positive airway pressure (PAP) on cognitive function in MS patients with OSA (Aim 2).

1.2 Background and Rationale

Cognitive dysfunction is one of the most common and disabling consequences of multiple sclerosis.

Multiple sclerosis (MS) is a chronic, autoimmune disease that causes inflammation and destruction of the brain and spinal cord. In addition to physical disability, MS patients suffer disproportionately from a variety of complications that negatively impact quality of life, including cognitive dysfunction.

Cognitive dysfunction is one of the most consequential symptoms of MS, spanning multiple domains of function including processing speed, working memory, learning, executive function, visual-spatial processing, and language function. It is experienced by 42-70% of MS patients and is a major cause of loss of employment, caregiver stress, and reduced quality of life.¹⁻⁵ Compared to individuals with MS who report only physical impairments, those with cognitive impairments are more likely to be unemployed and suffer from a mental illness, less likely to engage in social or vocational activities, and have more difficulty carrying out some activities of daily living. Even individuals with MS who are not considered to be “cognitively impaired” per se, and those whose functioning may remain in the normal range, may experience mild to moderate declines in cognitive functioning which could contribute to distress and functional impairments. Despite its impact, there are no definitive treatments for cognitive dysfunction in MS. While cognitive rehabilitation in MS may help to enhance information processing and general level of function, this approach is still considered relatively new, and its utility remains under investigation. Adjunctive treatments aimed at improving cognitive functioning are sorely needed. Furthermore, the identification of appropriate strategies to prevent and remediate cognitive dysfunction in MS is hindered by a poor understanding of clinical features that may influence its severity, or comorbidities that may increase patients’ vulnerability to its effects. *Further efforts are needed to identify and address clinical factors that could cause or exacerbate cognitive dysfunction in MS, and to identify patients who are most vulnerable to these effects.*

Obstructive sleep apnea (OSA) is a common and consequential medical disorder that causes cognitive dysfunction in the general population.

Obstructive sleep apnea (OSA) is a common disorder of sleep and breathing. The condition is characterized by repeated episodes of upper airway obstruction, hypoxia, and arousal during sleep. This growing epidemic is estimated to affect 10-20% of Americans, and is a well-recognized risk factor for many serious health consequences including hypertension, stroke, heart disease, and diabetes.^{15, 16} Obstructive sleep apnea also carries a profound societal impact in the form of daytime sleepiness, lost productivity, and absenteeism in the workplace.^{17, 18} The first-line treatment for OSA, Positive Airway Pressure (PAP), which is delivered by a mechanical device and mask interface, splints the upper airway open during sleep and effectively

ameliorates many of the symptoms caused by OSA. This air pressure can be continuous (CPAP), bi-level (BiPAP), or auto-adjusting (AutoPAP).

Obstructive sleep apnea is also an established cause of cognitive dysfunction in the general population.^{6-9, 11, 12 10} Sustained intermittent hypoxia that arises from OSA in non-MS patients has been linked to myelin and axonal injury, gray matter atrophy, as well as impaired executive function, long-term visual and verbal memory, visuospatial/constructional abilities, and attention.^{11, 19, 20 21, 22} Furthermore, treatment of OSA with PAP therapy has been shown to improve executive dysfunction, delayed long-term verbal and visual memory, attention/vigilance, global cognitive functioning, and gray matter volume in OSA patients without MS, *but the effect of OSA and its treatment with PAP therapy has not been studied in the context of comorbid MS.*

Clinical Rationale

Whereas the detrimental effects of OSA on cognition are well-established in the general population, the relationship between OSA and cognition has been virtually unstudied in patients with MS - a population that is particularly vulnerable to myelin and axonal damage by virtue of their neurological condition. This is a clinically relevant intersection, as MS is associated with a disproportionately high prevalence of OSA: new data from a recent study at our clinics show that at least 20% of MS patients suffer from clinically definite OSA, and up to 56% are at risk for OSA based on a validated screening tool (STOP-Bang).^{23, 24}

Furthermore, preliminary findings from the investigators suggest that sleep disturbances, and OSA in particular, could contribute to domains of cognitive dysfunction that are key aspects of morbidity in MS. If a causal role does exist, identification and treatment of OSA could provide new opportunities to improve cognition in MS patients. **This study will for the first time prospectively evaluate the effects of OSA severity and its treatment on multiple key domains of cognitive function most affected in patients with MS, while controlling for other sleep- and MS-related variables that may influence these relationships.**

Hypotheses

Hypothesis 1: Sleep apnea severity, as reflected by standard PSG measures [respiratory disturbance index (RDI), oxygen desaturation index (ODI), and minimum oxygen saturation (Min O₂)], as well as innovative new quantitative approaches, will be associated with reduced MACFIMS scores.

Hypothesis 2: Group 1, in comparison to Group 2, will show greater improvement from baseline in MACFIMS scores, on repeat MACFIMS testing at month 3.

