2.2 Endpoints

2.2.1 Primary Endpoint(s)

Effects of PSG-derived standard measures of sleep disordered breathing (including RDI, ODI, minimum O₂ saturation), on cognitive test scores.

Effects of PAP therapy on cognition, as measured by mean change from baseline in cognitive test scores in Group 1 (expedited PAP therapy) compared to Group 2 (delayed PAP therapy).

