2.2.2 Exploratory Endpoints

Effects of standard and novel PSG-derived measures of sleep disturbances (including TST, WASO, TAI, SE, RCREC, and sleep stage dynamics) on cognitive test scores.

Mean change from baseline in subjective sleepiness, as measured by the Epworth Sleepiness Scale, in group 1 vs group 2;

Mean change from baseline in daytime fatigue level, as measured by the Fatigue Severity Scale, in group 1 vs group 2;

Mean change from baseline in insomnia level, as measured by the Insomnia Severity Index, in group 1 vs group 2;

Mean change from baseline in quality of life and chronic daily symptoms (fatigue, anxiety, pain) as assessed by the Patient Reported Outcomes Measurement Information System (PROMIS, www.nihpromis.org/), in group 1 vs group 2.

[figure not shown]

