6.3 Baseline PSG visit*

Conventional In-lab Overnight Polysomnography (PSG): Procedures and scoring will follow the latest American Academy of Sleep Medicine Scoring Rules.²⁸ Standard measures will include: total sleep time (TST), sleep efficiency, sleep latency (SL [minutes from lights out to first 30 seconds of any sleep stage]), wake after sleep onset, total arousal index (TAI, average number of EEG arousals per hour of sleep), % total sleep time spent in stage 1, 2, 3, and REM sleep, the Respiratory Disturbance Index (RDI - total number of apneas, hypopneas and respiratory-related arousals per hour of sleep) central apnea index (total number of central apneas per hour of sleep), oxygen desaturation index (ODI, number of desaturation events $\geq 3\%$ below baseline oxygen saturation levels), minimum oxygen saturation (Min O₂), and % of sleep time with O₂ saturation $\leq 88\%$. PSG's will be scored by a single, experienced, technologist, masked to treatment group. Scoring will be reviewed and confirmed, and studies interpreted, by a board-certified sleep specialist.

Innovative PSG Signal Analysis Algorithms: In addition to conventional PSG measures, PSG data will also be analyzed using a novel PSG algorithm that has never been applied to sleep or cognitive research in MS patients. **This will involve no changes to the subject's overnight PSG procedure or experience.** This novel method, invented and patented by co-investigators Drs. [name] and [name],^{29, 30} uses variations in EEG power (for specific frequency bands) during discrete phases of the respiratory cycle (early expiration, late expiration, early inspiration, and late inspiration) to detect subtle, cortical microarousals not visible on standard visual inspection of the PSG.²⁸⁻³⁰ This algorithm will allow a more sensitive evaluation of potential effects that disordered nocturnal respiration could have on cerebral cortical function among MS patients. Specifically, respiratory cycle-related EEG changes (RCREC), which reflect cortical microarousals, will be computed to detect subtle disturbances in respiration beyond standard apnea/hypopnea measures, which will then be correlated with MACFIMS scores.

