7.2 Exploratory

Measures of sleep quality and sleep fragmentation, as well as Innovative PSG Signal Analysis Algorithms (secondary predictors of cognitive performance), will be assessed with overnight polysomnography (see section 6.3).

Epworth Sleepiness Scale (ESS): The ESS is an 8-item questionnaire that asks about the likelihood of dozing in variably sedentary situations.³¹ This commonly used measure of subjective sleepiness, or sleep propensity, is reliable, internally consistent, and validated against objective polysomnographic measures. A score ≥ 10 suggests excessive sleepiness.

Krupp's Fatigue Severity Scale (FSS): The FSS is a validated, 9-item instrument that measures the impact of fatigue on multiple outcomes, with a physical focus.³² Prior studies have shown acceptable internal consistency and stability over time, and sensitivity to change that correlates with the subject's clinical improvement. Many if not most past studies on MS-related fatigue have used the FSS.

Insomnia Severity Index (ISI): The Insomnia Severity Index (ISI) is a 7-item questionnaire with 5-point Likert scale responses designed to assess the nature, severity, and impact of insomnia in adults.³³ Scores of 15 or higher reflect moderate clinical insomnia.

Patient Reported Outcomes Measurement Information System (PROMIS)/Quality of Life in Neurological Disorders (NeuroQoL): The federally-funded Patient Reported Outcomes Measurement Information System (PROMIS) and Quality of Life in Neurological Disorders (NeuroQoL) are two integrated systems of highly reliable and responsive assessment tools that use modern measurement theory to assess patient-reported health related quality of life. Using validated item banks and standardized metrics, PROMIS and NeuroQoL reliably measure patient-reported outcome measures (PROM's) for clinical research. PROMIS and NeuroQoL measures, derived from large question banks, can be given as static short forms (typically 7-8 items in length). Measures can be used as primary or secondary endpoints in clinical studies that assess treatment effect for multiple symptoms including quality of life, pain, anxiety, fatigue and sleep quality (www.nihpromis.org/; www.neruoqol.org).

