9.0 DATA ANALYSIS/STATISTICAL METHODS

9.1 Sample Size Determination

Estimates (means and standard deviations) are derived from our recent data that evaluated SDMT scores among MS subjects referred for overnight PSG, and previously published interventional studies in that evaluated the effects of medical interventions on components of the MACFIMS in MS patients. We have chosen to focus on SDMT score as the primary outcome variable of interest, as the SDMT encompasses multiple domains of cognitive function, is frequently used in MS clinical studies as a reliable measure of cognitive impairment, and is sensitive to changes in intervention.

Based on a power analysis of two sample means (unequal sample sizes, with 2:1 randomization) with a 0.05 two-sided significance level, and an estimated S.D. of 9, a total sample size of 140 subjects will have an 86.3% power to detect a 5-point difference in SDMT score between groups, on month 3 testing, for hypothesis 2. Similarly, using individual MACFIMS components as outcome variables (in separate models), a multiple linear regression power analysis shows that a sample size of n=140 subjects will yield 88% power to detect an R-square difference of 0.05 for the test predictor of interest (% PAP use per month, as a continuous measure), assuming the R-squared explained by the adjustment variables is at least 0.3.

Although we predict a low dropout rate due to the short duration of the study, if we assume a dropout rate of 15% (10 dropouts per group), we will still have a power of 81.2% power to detect a 5-point difference in SDMT score between groups, on month 3 testing.

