9.2 Analysis of Primary Endpoint

Aim 1: Multivariate linear regression models will be used to analyze the effects of baseline PSG-derived standard measures of sleep disordered breathing (including RDI, ODI, minimum O2 saturation), on individual cognitive test scores (continuous outcome variables of interest, in separate models) for Aim 1, controlling for other sleep, serological, and clinical variables. Additional models that use computed respiratory cycle-related EEG changes (calculated as the maximum difference between the mean EEG powers associated with each of the 4 respiratory cycle segments as predictor variables) will be used to evaluate the effects of respiratory-related cortical microarousals on cognitive test scores, controlling for other clinical and sleep-related variables. Separate models that use computed temporal patterns of sleep stages as predictors of cognitive test scores will also be constructed.

Aim 2: Multivariate linear regression models will be used to test the effects of Group effect on 3-month (“post”) cognitive test scores, controlling for baseline (“pre”) test scores. We will also examine the association of PAP use as a continuous variable, based on mean nightly hours of use per month, on 3-month individual cognitive test scores, controlling for baseline scores. Separate models will be used for each cognitive test of interest. Predictor variables that are unbalanced between groups despite randomization will be used as covariates in the analyses.

To evaluate early effects of PAP therapy on cognitive scores, sleep stage dynamics will also be assessed during PAP titrations to determine whether changes in sleep stage stability predict improvements on cognitive test scores in separate models.

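### Aim 1, a primary endpoint, tests several PSG measures against every cognitive score with no single primary measure and no error control, and the novel PSG measures are primary in Hypothesis 1 and Section 9.2 but exploratory in 2.2.2 and 7.2

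*Combined protocol and SAP*

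**What the plan says.** Section 2.2.1 has two primary endpoints. The Aim 1 endpoint is "Effects of PSG-derived standard measures of sleep disordered breathing" on cognitive test scores, with RDI, ODI and minimum oxygen saturation given as an open list.

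Section 7.1 names sleep apnea severity as the primary predictor, measured by polysomnography, but does not say which PSG measure represents it.

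Section 9.2, headed as the analysis of the primary endpoint, regresses individual cognitive scores on these measures, with a separate model for each score. Under the same Aim 1 heading it adds RCREC models that "will be used to evaluate the effects of respiratory-related cortical microarousals on cognitive test scores" and further models using sleep-stage patterns.

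The novel measures are placed as follows:

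- **Hypothesis 1 (Section 1.2):** the standard measures, "as well as innovative new quantitative approaches, will be associated with reduced MACFIMS scores".
- **Section 2.2.2, among the endpoints classed as exploratory:** "Effects of standard and novel PSG-derived measures of sleep disturbances (including TST, WASO, TAI, SE, RCREC, and sleep stage dynamics) on cognitive test scores".
- **Section 7.2, headed Exploratory:** PSG sleep-quality measures, "as well as Innovative PSG Signal Analysis Algorithms (secondary predictors of cognitive performance".
- **Section 6.3, on RCREC:** "This novel method, invented and patented by co-investigators".

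Section 9.1 names SDMT as the primary outcome variable, then gives power for Hypothesis 2 and for PAP use. Sections 2.2.1, 7.1 and 9.2 do not apply SDMT to Aim 1. The only significance level in the plan belongs to the group comparison: "with a 0.05 two-sided significance level, and an estimated S.D. of 9".

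**The concern.** Aim 1 carries primary rank, but the plan does not say which result would confirm or refute Hypothesis 1. It has at least three predictors, each crossed with every cognitive score, and nothing ranks these pairs or limits the overall false-positive rate. An author who followed the plan exactly could pick out whichever pair was significant and call it a primary finding.

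The placement of the novel measures makes this worse. An RCREC result could be reported as primary by citing Hypothesis 1 and Section 9.2, or as exploratory by citing 2.2.2 and 7.2. Co-investigators hold a patent on the RCREC method, so its rank should be settled before the data are analysed.

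The point concerns Aim 1 and its predictors. It does not dispute the randomised comparison on SDMT.

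**Working it through.** **1. The plan's own figure.** No power or significance level is given for Aim 1. The nearest figure, for Aim 2, is "a total sample size of 140 subjects will have an 86.3% power to detect a 5-point difference in SDMT score between groups". With 93 and 47 subjects, SD 9 and a difference of 5:

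- Standard error = 9 × √(1/93 + 1/47) = 1.61.
- Ratio = 5/1.61 = 3.10.
- Power = 87.4% (normal) or 86.9% (noncentral t), against 86.3% stated.

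The figure is reproduced to within about a point. It says nothing about Aim 1.

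**2. Counting the Aim 1 tests.** There are three named standard measures. The number of outcomes depends on the reading:

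- SDMT only, if 9.1 governed Aim 1: 3 × 1 = 3 tests.
- The 7 standard measures that Section 6.2 attributes to MACFIMS: 3 × 7 = 21 tests.
- The scores listed in 6.2 without NAART and the Nine-hole Peg Test: SDMT 1, PASAT 2, CVLT-II 2, BVMT-R 2, JLO 1, COWAT 1, Trails 2, Go/No-go 2, total 13. This gives 3 × 13 = 39 tests.

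**3. Chance of at least one false positive at two-sided 0.05 per test.** For m independent tests this is 1 − 0.95^m. PSG measures and cognitive scores are correlated, so it was also simulated under no association at n=175. The documents give no correlations. The ranges below assume 0.5–0.8 among predictors and 0.3–0.7 among scores.

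| Family | Tests | Independent | Correlated |
|---|---|---|---|
| 3 measures, SDMT | 3 | 14% | 9–13% |
| 3 measures, 7 outcomes | 21 | 66% | 31–56% |
| 3 measures, 13 scores | 39 | 86% | 41–76% |

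The expected number of false positives does not depend on correlation: 39 × 0.05 = 1.95 for the largest family.

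**4. Adding the novel measures.** Counting RCREC and sleep-stage dynamics as one predictor each gives five predictors. On SDMT that is 5 tests, 1 − 0.95^5 = 23% if independent. On 7 outcomes it is 35 tests, 83% if independent and 39–64% with predictors at 0.5–0.8 and scores at 0.5–0.7.

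**5. Counting only the hypothesised direction.** Hypothesis 1 predicts reduced scores. If results in the other direction are set aside, the rates for the three standard measures are roughly halved: about 4–6.5% for 3 tests, 15–30% for 21, and 28–43% for 39 at score correlations of 0.3–0.5. The matching nominal level is 2.5%.

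**6. Power after a fix.** Section 9.1's R-square inputs for PAP use are borrowed here, and 5 covariates are assumed. Then f² = 0.05/(1 − 0.30 − 0.05) = 0.077 and noncentrality = 175 × 0.077 = 13.5. Power is about 95% for one test at 0.05, 89% at 0.05/3 = 0.0167, and 72% at 0.05/21 = 0.0024.

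**The case against.** The strongest reply is that the plan already has a hierarchy. Section 2.2.1 restricts the primary endpoint to standard measures. Sections 2.2.2 and 7.2 agree with each other, because the phrase about secondary predictors sits under the Exploratory heading. Section 9.2 introduces the novel models as additional and separate. A reader might infer three competing ranks, but the text supports only two: primary or exploratory. That conflict stands, because Hypothesis 1 and the heading of 9.2 do not follow 2.2.1. Section 9.3 does not resolve it either, since it covers only group effects on patient-reported outcomes.

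A second reply is that 9.1 already chooses SDMT. If that governed Aim 1, the family would be three tests and the inflation modest. But the choice is made in the sample-size section, which powers Hypothesis 2 and PAP use, and 9.2 does not apply it to Aim 1. Even three tests exceed 5%.

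Third, a reader might infer that with no true association the plan would more often than not yield a finding for Hypothesis 1. The documents do not support this as a general statement. It depends on counting 13 or more scores, on assumed correlations, and on accepting either direction. With the standard measures and only the hypothesised direction counted, the simulated values stay below 50%.

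Two further readings go too far. The plan does name a primary predictor, as a construct; what it lacks is a single PSG measure of it. The patent statement covers RCREC; Section 6.3 credits the sleep-dynamics work to the study team without mentioning a patent.

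Finally, Aim 1 is a baseline association analysis, not the randomised comparison. That lowers the severity, but 2.2.1 still gives Aim 1 primary rank.

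**Conclusion.** The point holds and should be fixed. The primary Aim 1 analysis has no single primary PSG measure, significance level, testing order or multiplicity adjustment, and the novel measures are inside it in two places and outside it in three.

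The size depends on which outcomes count. For the standard measures the two-sided chance of at least one false positive is about 9–13%, 31–56% or 41–76% for 3, 21 or 39 tests. These figures rest on assumed correlations, an assumed count of scores and n=175. In every two-sided case the rate exceeds the nominal 5%. The conflict over the novel measures depends on none of these assumptions.

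Nothing here challenges the stated sample size or the Aim 2 power.

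**What to change.** 1. Remove the clause on novel approaches from Hypothesis 1, or make it a separate exploratory hypothesis. Move the RCREC and sleep-stage models from 9.2 to 9.3, to match 2.2.2.
2. State in 2.2.1 and 9.2 that SDMT, already the primary outcome variable in 9.1, is the Aim 1 primary outcome. Before analysis, either name one PSG measure (for example RDI, already the stratification factor) tested at two-sided 0.05, or test RDI, ODI and minimum oxygen saturation on SDMT with Holm. Other prespecified hierarchies would also serve; what matters is that one is written down.
3. Report all other predictor-by-score pairs as secondary or exploratory, for example with false-discovery-rate control.

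The cost is wording in Hypothesis 1, 2.2.1, 9.2 and 9.3, with no new data. Under the borrowed inputs, power at n=175 stays at about 95% for one test and about 89% for a given measure at the strictest Holm step. The downside is that fewer Aim 1 results can be called confirmatory.
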